5.2 Changes from Protocol Specified Analyses

Any changes to analysis as a result of changes to the protocol, or updates to the analysis methods will be documented in this SAP, or as an amendment after this SAP has been finalized.

Changes

- As agreed with FDA in post IDE-approval discussions, the randomization is stratified by region (North America vs ROW). As discussed further below, the statistical model will evaluate the fixed effect of region and treatment-by-region interaction.

5.3 Efficacy Endpoints

The primary endpoint will be the change of the FMA UE score from Visit 4 (pre-therapy, baseline) to Visit 5 (Day 1 post therapy).

There are three hierarchical secondary endpoints

1. The proportion of responders, defined as a 6-point change or greater in the FMA UE score from baseline (Visit 4) to Day 90 post treatment (Visit 7)

2. The change in WMFT from baseline (Visit 4) to Day 90 post treatment (Visit 7)
3. The change in FMA UE score from baseline (Visit 4) to Day 90 post treatment (Visit 7)

Quality of Life Endpoints

Quality of life assessments and a motor activity log will be used to provide data to support overall treatment response:

- Stroke Impact Scale (SIS): The SIS has been developed to assess eight different domains of health-related quality of life, such as emotion, communication, memory, and thinking, and social role function. Each item is rated on a 5-point Likert scale in terms of the difficulty the person has experienced in completing each item. Scores for each domain range from 0-100.
- Stroke Specific QOL (SS-QOL): The SS-QOL is a self-report questionnaire consisting of 49 items in the 12 domains of energy, family roles, language, mobility, mood, personality, self-care, social roles, thinking, upper extremity (UE) function, vision, and work/productivity.
- 5Q-5D QOL (general QOL) – EQ-5D™ is a standardized instrument for use as a general measure of health outcome. It provides a simple descriptive profile and a single index value for health status.
- Motor Activity Log (MAL) - The MAL consists of 14 activities (patient reported outcomes) of daily living (ADLs) such as using a towel, brushing teeth, and picking up a glass. For a specified time period post-stroke, the individual is asked about the extent of the activity performed and how well it was performed by the more impaired arm. The response scale ranges from 0 (never used) to 5 (same as pre-stroke).

These QOL measures are considered “tertiary” or “other” endpoints that provide further evidence of the benefits of treatment (not considered primary or secondary endpoints).

5.4 Study Hypothesis Testing

The primary objectives are to assess the efficacy and safety of 6 weeks of VNS therapy performed during rehabilitation for subjects with upper limb motor deficits following stroke. .

The primary efficacy analysis will be based on the change of the FMA UE score from baseline (Visit 4) to Visit 5 (Day 1 post therapy). The null hypothesis is the change in FMA UE is not different between VNS treatment and control sham treatment, with significance at alpha 0.05 two sided.

Three secondary endpoints will each be tested for significance with 0.05 Type I error (two sided) in a hierarchical manner. Significance will be declared for the first secondary endpoint at 0.05 only if the primary is significant at 0.05, and each subsequent endpoint only if all higher ranked endpoints were significant at 0.05.

5.5 Handling of Missing Values and Outliers

All data collected under this protocol will be included in the assessment of safety. For AEs missing severity and relationship, if there is no other information available, relationship will be assessed as “possible” and severity will be assessed as “severe” for summary purposes, unless there is specific justification presented to impute other values. Missing or incomplete start dates will be imputed to the date of device implantation. Outliers that may have undue influence on the analysis and results will be discussed, but the results will not be based on any exclusion.

For the analysis of the efficacy endpoints, missing data will be imputed with a Last Observation Carried Forward approach. For any missing Visit 4 baseline data; the Visit 2 measure will be used as baseline. Multiple imputation, with missing at random assumptions using SAS PROC MI will also be performed as a sensitivity analysis. Data from the control group will be used to impute the missing in the VNS group. The specific imputation model will be defined prior to database lock. For the responder analysis, subjects with missing results will be imputed as non-responders for the initial evaluation, and a tipping point analysis will be used to assess sensitivity to missing data.

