2.1 Primary Objective

The primary objectives of this study are to assess:

- the efficacy of VNS therapy compared to standard rehabilitation (active control includes the surgical intervention and sham stimulation) in the recovery of upper limb motor function after stroke.
- safety of the surgical intervention and VNS stimulation

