3.3 Study Schedule and Treatment

Stage I: Subjects will be screened and assessed for upper limb paresis associated with stroke using a detailed stroke history evaluation (including type, location, onset, neurological evaluation, etc.) and various assessment scores to determine the level of disability in performing everyday tasks. Clinical evaluations by a stroke expert will confirm subjects entering the study exhibit a moderate to severe motor impairment in the upper extremity (UE) (as indicated by a FMA-UE score of 20 to 50) and have at least a nine-month history of the disorder. After informed consent signature, repeat assessments and other measurements will be recorded prior to randomization. Subjects will maintain their group assignments through Visit 7 (end of Stage I, assessment follow-up).

Subjects will start study therapy after an approximately one-week recovery period after surgery. This time period may vary depending on schedules and subject recovery times. The assessments after surgery, and before treatment (Visit 4) will be the baseline for statistical analyses. After a 6 week acute treatment period, post treatment assessments will be done at Visit 5 (1 Day post treatment), Visit 6 (30 Days post treatment), and Visit 7 (90 Days post treatment). During this 90 day post treatment period, subjects will not receive in-clinic rehabilitation, but are given a magnet to swipe just prior to performing their in-home rehabilitation for 30 minutes daily. The magnet activates VNS in the VNS group subjects but does not activate VNS in the Control subjects.

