5.13 Safety Analyses

The safety endpoints in this study include adverse events, device complications, and the Beck Depression Inventory (BDI). Other assessments, including Neurological Examinations, and Physical Examinations will be summarized.

Safety analyses will be based on the ITT population.

The safety results will be reported overall and for each of the following study phase:

- study entry through surgery
- through treatment to visit 5

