5.13.1 Adverse Events

Adverse Events (AEs) are defined as any undesirable medical occurrence in a study participant, whether or not considered related to the study devices or procedure, which is identified or worsens during the clinical study.

Serious Adverse Events (SAEs) are defined as adverse events that result in death, are life threatening, require inpatient hospitalization greater than 24 hours, or prolongation of an existing hospitalization, require intervention to prevent permanent impairment/damage, or result in persistent or significant disability/incapacity.

Serious Unanticipated Adverse Device Events (SUADEs) are defined as serious adverse experiences directly related to the use of the investigational device leading to injury, illness, or death of a study participant not previously identified in nature, severity or degree of incidence in the protocol.

Adverse Events will be reported by the investigator and will be tabulated by treatment group. Summaries by relatedness to device and surgery, as well as severity, will be provided. SAE and SUADEs will also be summarized by treatment group.

Listings of AE, SAE, and SUADE data will be provided to supplement the tabulated results.

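### Incomplete AE start dates are all set to the implant date, even when the recorded month proves later onset, which can misplace events in the by-phase safety tables (minor)

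*SAP*

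**What the plan says.** SAP section 5.5 deals with three AE fields in consecutive sentences.

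- Severity and relationship get default values under a condition: "For AEs missing severity and relationship, if there is no other information available". That sentence also lets a specific justification override the default.
- Start dates get a flat rule: "Missing or incomplete start dates will be imputed to the date of device implantation". It carries no condition and no exception for a known month or year. The sentence does not name AEs, but it directly follows the AE sentence in a paragraph on safety data, so AE start dates are the natural subject.

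Section 5.13 then splits the safety output by time: "The safety results will be reported overall and for each of the following study phase", followed by two phases, "study entry through surgery" and "through treatment to visit 5". Section 3.1 places randomization on the day of implant surgery, so the implant date is the surgery date and falls in the first phase.

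Section 5.13.1 adds tabulation by treatment group and, separately, "Summaries by relatedness to device and surgery, as well as severity, will be provided". Section 2.1 lists "safety of the surgical intervention and VNS stimulation" among the primary objectives.

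**The concern.** A date can be incomplete and still be informative. If the month and year are recorded and only the day is missing, they may show that the event began weeks after surgery. The rule discards that information and assigns a date that the record excludes. The neighbouring sentence on severity and relationship uses other available information before it falls back on a default; the start-date sentence does not.

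What is at stake is the split of AEs between surgery and the time after it. Section 2.1 asks about the safety of both the surgery and the stimulation, and the phase tables are where the SAP separates AEs by time. An event moved back to the implant date adds to the surgery phase and is lost from the period in which it occurred.

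**Working it through.** The SAP gives no figure on this point, so there is nothing to reproduce. The check has a logical part and an illustrative count.

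**Logic, by example.** Take an implant on 10 March and an AE recorded as April of the same year with the day missing.

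- Earliest possible onset: 1 April, which is 22 days after surgery.
- Date under section 5.5: 10 March.
- Phase, if assigned by start date: "study entry through surgery".
- The recorded month excludes that phase.

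A partial date in a month before the implant is also overwritten, by moving it forward to the implant day, but that event stays in the same phase.

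**Illustrative count.** The question is how often the month alone rules out the implant date when month and year are known and the day is missing.

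Inputs:
- Recovery before therapy of about 7 days (section 3.3: "Subjects will start study therapy after an approximately one-week recovery period after surgery").
- Six weeks of therapy, with Visit 5 one day and Visit 7 ninety days after it (section 3.3). Visit 5 is therefore at day 7 + 42 + 1 = 50 and Visit 7 at day 7 + 42 + 90 = 139.
- Assumptions: every implant date in a 365-day year is equally likely, and onset is equally likely on each day of the stated window.

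For onset *d* days after implant, the number of the 365 implant dates whose onset falls in a later calendar month is:
- *d* = 1 to 28: 12 × *d* (the last *d* days of each month)
- *d* = 29: 11 × 29 + 28 = 347
- *d* = 30: 11 × 30 + 28 = 358
- *d* ≥ 31: 365

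Summing over the window and dividing by 365 × (days in the window):

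| Onset window | Later month / all pairs | Share |
|---|---|---|
| Days 1–7 | 12 × 28 = 336 / 2,555 | 13.2% |
| Days 1–14 | 12 × 105 = 1,260 / 5,110 | 24.7% |
| Days 1–50 (to Visit 5) | 4,872 + 347 + 358 + 20 × 365 = 12,877 / 18,250 | 70.6% |
| Days 51–139 (Visit 5 to Visit 7) | 32,485 / 32,485 | 100% |

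Recovery length matters little. For the window from surgery to Visit 5, 5 days of recovery gives 12,147/17,520 = 69.3% and 21 days gives 17,987/23,360 = 77.0%. Onset timing matters far more: the share falls from about 71% to about 13% if events cluster in the first week after surgery.

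**Residual error of the fix.** Suppose a partial date in a later month is set to the first of that month. An event with onset after Visit 5, but in the month containing Visit 5, is then dated on or before Visit 5. With *e* days from Visit 5 to onset, the same-month count is 365 − 12*e* for *e* = 1 to 28, then 18, then 7, then 0. The total is 5,348 + 18 + 7 = 5,373 of 32,485 pairs, or 16.5% of onset days between Visit 5 and Visit 7.

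**The case against.** Four arguments can be made for leaving the rule alone.

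- **The link to the phase tables is inferred.** Section 5.13 does not say that phase is assigned by AE start date, and it gives the second phase no explicit starting point. If that phase were cumulative from study entry, an event dated at implant would still be in it. This stands as a caveat. Two consecutive phases split by start date is the more natural reading, but the conclusion depends on it.
- **The main safety outputs are untouched.** Overall tables by arm, relatedness to device and surgery, and severity do not depend on start date, and listings are also provided. No test is specified on the phase tables. This stands and limits the point to a descriptive split.
- **The number of events may be nil.** The SAP does not say how many start dates are expected to be incomplete. This stands too.
- **The implant date is a defensible default for a wholly missing date.** It keeps the event in the study. This is accepted; the complaint covers only partial dates whose known parts exclude the implant date.

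A reader might go further and infer that about 71% of incompletely dated events are misclassified, or that the rule moves that share out of the stimulation period. The document supports neither. The 71% applies only to dates missing just the day, under even onset up to Visit 5. That window also includes the recovery week before therapy starts, so some of the moved events did not begin during stimulation.

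**Conclusion.** The rule is wrong as written for partial dates whose recorded month and year exclude the implant date, because it replaces recorded information with a date known to be false. On the natural reading of section 5.13, it overstates surgery-phase AEs and understates later ones.

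The point is minor. It is confined to descriptive tables and affects an unknown, possibly zero, number of events. Depending on when events begin, the month rules out the implant date for anything from about 13% to about 71% of day-missing dates with onset up to Visit 5. These are illustrations under stated onset patterns, not estimates for this trial.

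A reader might also infer that the rule distorts the overall safety comparison between arms. It does not: those counts do not change when an event's date moves.

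**What to change.** Amend the start-date sentence in section 5.5 so that no imputed start date contradicts recorded date parts:

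- Use the implant date only when the start date is wholly missing, or when its known parts are compatible with the implant date.
- Otherwise use the earliest date consistent with the known month and year.

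The cost is one clause in the SAP and minor programming, with no new data.

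Two limits remain. Partial dates in the implant month stay in the surgery phase because the record cannot separate them; under even onset to Visit 5 these are 100% − 70.6% = 29.4% of day-missing dates. Some events with onset after Visit 5, in the month containing Visit 5, would be dated on or before that visit (16.5% of onset days between Visit 5 and Visit 7 in the illustration). Under the present rule all of those events go to the implant date, so the change still leaves fewer events in the wrong phase.

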5.6 Final Stage I Analyses, and Unblinding

The final Stage I analysis will be generated after the blinded portion of the database has been locked (after the last subject completes Stage I, which excludes additional long-term follow-up after that point) and the data are unblinded.

In the case of an emergency or unplanned need for unblinding, with proper documentation and authorization from MicroTransponder, Inc. management, the treatment assignment only for the specific subject to be unblinded will be released. Any unblinding will be documented with a note on the Treatment Assignment List as well as appropriate memos to the study file.

5.7 Pooling of Sites and Regions

Because of the relatively small sample size for each treatment group, all sites will be pooled within region (all US sites will be pooled into one region and all UK sites will be pooled into a second region). A treatment by region interaction term will be included in the ANCOVA model, and tested at 0.10 alpha. If the interaction term is not significant at $p < 0.10$, the primary analysis will be performed with a reduced model that does not include the treatment by region term.

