3.4 Sample Size Calculation/Justification

The study plan is to enroll and implant up to 120 subjects in order to have approximately 100 subjects complete the study. A sample size of 100 subjects total (50 per group) will have 80% power with 0.05 alpha to detect a difference of 2.3 with SD=4.0 on the FMA UE scale between the two treatment groups. This is based on the assumption of VNS having an average improvement of 7.5 from baseline, with control having an average change of 5.2 from baseline. A sample size of 50 per group will have over 95% power at 0.05 alpha to show a difference in responders (defined as an improvement of 6 points or more from baseline), assuming 75% response in the VNS group and 33% in the control group. With respect to safety, a sample of at least 100 subjects implanted and receiving VNS allows adequate power to detect the incidence of safety and device events. A sample of 100 subjects yields 95% probability that the study will reveal at least one occurrence of all events or complications that occur in subjects at a rate of 3% or greater. In addition, implantation and follow-up of 100 subjects for 6 weeks will yield 4200 subject-days (600 weeks or over 11 years) of total exposure.

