4 ANALYSIS SETS & SCHEDULE

4.1 Intent to Treat (ITT)

The ITT population will include any subject who is randomized, and will be the basis of the efficacy and safety analyses. All subjects who undergo surgery will be included in the safety population, with all adverse event and safety information reported.

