5.12 Efficacy Analyses

The primary efficacy endpoint will be the UE Fugl-Meyer Assessment (FMA UE) with focus on the change from Visit 4 (baseline), to Visit 5 (Day 1 post in-clinic therapy). An analysis of covariance (ANCOVA) model will be used, with the change from baseline as the dependent variable, and the treatment, region, treatment by region interaction as factors, with age and baseline FMA UE score as covariates. The treatment by region interaction will be removed if $p > 0.10$.

In addition, as a sensitivity analysis of the FMA UE data across all visits, a Mixed Model Repeated Measures (SAS PROC MIXED) analysis will be used to evaluate the differences between treatment from Visit 4 through Visit 7 (end of Stage I). An unstructured covariance structure will be assumed, with the same factors and covariates as in the ANCOVA. This mixed model will also allow for missing data assuming missing at random.

Secondary Endpoints

1. FMA UE Responder at Day 90 - A responder analysis will be performed for the UE Fugl-Meyer with the definition of response defined as ≥ 6 point change from Baseline (Visit 4) to Visit 7 (Stage I). The proportion of subjects in each treatment group that meet or exceed the Responder definition will be determined and summarized by visit, including a 95% binomial confidence interval. Responder rates will be tested for differences between treatment groups using logistic regression, with treatment and randomization strata as factors. Other cut-off points for classification as a responder will be considered for a sensitivity analysis.
2. WMFT Change from baseline to Day 90 - This analysis will be based on the change in WMFT score from Baseline (Visit 4) to Day 90 (Visit 7). This will be done using ANOVA, with treatment and randomization strata as factors. Sensitivity analysis will not be done.

3. FMA UE Change from Baseline to Day 90 - This analysis will be done using the same model as for the primary endpoint, but with the change from Baseline to Day 90 as the dependent variable.

Other Endpoints

The QOL assessments, BDI and Motor Activity Log will be summarized by treatment group for each visit at which the assessment is collected, as well as the change from baseline to each visit. Because of the large number of assessments and domains, only summary statistics will be presented.

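### A 0.10-level region interaction test selects the primary model, and no treatment contrast is named if the interaction stays, so the two-sided 0.05 level is not assured

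*SAP*

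**What the plan says.** - **Model.** Section 5.12 fits an ANCOVA to the change in FMA-UE from Visit 4 to Visit 5, with "the treatment, region, treatment by region interaction as factors" and with age and baseline FMA-UE as covariates.
- **Selection rule.** "The treatment by region interaction will be removed if" its p-value is above 0.10 (Section 5.12). Section 5.7 gives the same rule: without significance at 0.10, "the primary analysis will be performed with a reduced model that does not include the treatment by region term". Neither section says what the primary test is when the term is kept.
- **Background to the term.** Section 5.2 records stratification by region as agreed with FDA, and then says that "the statistical model will evaluate the fixed effect of region and treatment-by-region interaction". It gives no region weighting.
- **Level.** Section 5.4 tests the primary null of no difference between VNS and control "with significance at alpha 0.05 two sided". It opens the three ordered secondary tests only if the primary succeeds.
- **Reuse.** For the Day 90 FMA-UE secondary, "This analysis will be done using the same model as for the primary endpoint". The repeated-measures sensitivity analysis also takes over the ANCOVA's factors and covariates.

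**The concern.** With a treatment-by-region term in the model there is no single treatment effect. At least three contrasts could be reported as the treatment test:

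- the average of the two regional effects with equal weight (assumed here to be what a default SAS Type III test gives);
- the average weighted by the number of subjects;
- the effect in one reference region.

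These are different hypotheses and can give different p-values. Under the first and third, the trial moves to a differently weighted estimate exactly when the regions look different. That selection is not allowed for in the 0.05 level. The primary test is also the gate to all three secondaries, so an excess there carries into the hierarchy. Because the branch is undefined, the confirmatory contrast could be settled after unblinding.

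**Working it through.** **Inputs.** From the SAP: difference 2.3, SD 4.0 and 50 per group (3.4); 1:1 allocation (3.1); two-sided 0.05 (5.4); interaction level 0.10 and two regions (5.7). Assumed: 1:1 within region and no true interaction. The region split is not stated, so 50/50 to 90/10 is shown.

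**1. The plan's own power.** The standard error is 4 × √(2/50) = 0.8, so the noncentrality is 2.3/0.8 = 2.875. Power is 0.812 (noncentral t, 98 df) or 0.820 (normal approximation). The stated 80% is reproduced.

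**2. Why the contrast matters.** With n₁ and n₂ subjects in the larger and smaller region (N = n₁ + n₂), regional difference dᵣ has variance 4 × 16/nᵣ = 64/nᵣ. The interaction estimate is d₁ − d₂. The absolute correlation of each contrast with it is:

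- equal-weight: (n₁ − n₂)/N;
- subject-weighted: 0, because n₁ × 64/n₁ − n₂ × 64/n₂ = 0;
- larger region alone: √(n₂/N); smaller region alone: √(n₁/N).

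| Split | Equal-weight | Subject-weighted | Larger region | Smaller region |
|---|---|---|---|---|
| 50/50 | 0 | 0 | 0.71 | 0.71 |
| 70/30 | 0.40 | 0 | 0.55 | 0.84 |
| 80/20 | 0.60 | 0 | 0.45 | 0.89 |
| 90/10 | 0.80 | 0 | 0.32 | 0.95 |

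A contrast uncorrelated with the pre-test is essentially untouched by it. A correlated one is tested mostly when it is already extreme.

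**3. Type I error of the two-step rule.** N = 100, 4,000,000 simulated trials per setting, residual df 94 with the interaction and 95 without, term kept if p < 0.10:

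| Split | Fixed, no interaction | Equal-weight | Subject-weighted | Larger region | Smaller region |
|---|---|---|---|---|---|
| 50/50 | 0.0502 | 0.0506 | 0.0506 | 0.0705 | 0.0705 |
| 60/40 | 0.0501 | 0.0521 | 0.0505 | 0.0662 | 0.0749 |
| 70/30 | 0.0500 | 0.0566 | 0.0505 | 0.0621 | 0.0797 |
| 80/20 | 0.0500 | 0.0645 | 0.0504 | 0.0581 | 0.0849 |
| 90/10 | 0.0500 | 0.0767 | 0.0504 | 0.0543 | 0.0908 |

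With equal weighting, false positives favouring VNS are 2.5%, 2.8%, 3.2% and 3.8% at 50/50, 70/30, 80/20 and 90/10, against a nominal 2.5%.

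**4. Where the excess arises.** A separate simulation (100,000 full ANCOVA fits per split) kept the term in about 10% of null trials. Among those, the equal-weight contrast rejected in 5.8%, 11.1%, 20.5% and 32.8% at the same four splits. At 80/20 this gives about 0.90 × 0.050 + 0.10 × 0.205 = 0.0655, against 0.0653 simulated directly.

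**5. Check with covariates.** A further 60,000 full ANCOVA fits per split, with age and baseline FMA-UE in the model, gave equal-weight type I error of 0.0490, 0.0568, 0.0644 and 0.0762.

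**6. Power at a uniform 2.3 points.** The fixed model has 0.812. The rule with equal weighting has 0.813, 0.801, 0.787 and 0.781 at the four splits; with subject weighting it has 0.813 throughout.

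**7. Larger analysis set.** The plan is to "enroll and implant up to 120 subjects in order to have approximately 100 subjects complete the study", and the ITT set "will be the basis of the efficacy and safety analyses", so up to 120 may be analysed. Equal-weight type I error is then essentially the same: 5.0%, 5.7%, 6.4% and 7.7%. Power is 0.878 fixed, against 0.878, 0.866, 0.850 and 0.840.

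**The case against.** The strongest reply is that the pre-test does little harm by itself. With a subject-weighted contrast the rule keeps 5.0–5.1% at every split, so the only real gap is an unnamed contrast in a branch entered in about 10% of null trials. That diagnosis is right. But the SAP does not name that contrast, and the equal-weight alternative does exceed 5% when regions are unequal.

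Second, the size rests on a split the SAP does not give. With equal weighting the excess is about 0.1 points at 50/50 and 0.2 at 60/40, and nothing in the document makes 80/20 or 90/10 likely. This stands as a limit on what can be claimed.

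Third, the single-region reading is strained, because Section 5.4 states the null for VNS against control overall. This also stands: those figures are the least natural reading, and the conclusion does not need them.

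Fourth, naming a subject-weighted contrast would be a smaller edit than taking the interaction out of the primary model. That is a fair alternative.

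Finally, the FDA discussions might be cited in defence of the rule. Section 5.2 attributes the regional stratification to that agreement and then describes evaluating the interaction. It does not say that the interaction should choose the primary test.

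**Conclusion.** The concern holds. The primary analysis has two branches and the treatment test is defined in only one, so the 0.05 level is not assured. It is not shown to be exceeded. Under equal weighting, type I error runs from 5.1% at 50/50 to 7.7% at 90/10. Under subject weighting there is essentially no inflation. Under both equal-weight and single-region readings, the region weighting of the reported effect would depend on the pre-test. The power cost with equal weighting is small: at most about 3 points with 100 subjects and 4 with 120.

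These figures assume SD 4, 1:1 allocation within region and no true interaction, over an assumed range of splits. If the regions truly differ, the undefined branch is reached more often. This is a real but conditional weakness in the primary test, and cheap to close before unblinding.

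**What to change.** In Sections 5.7 and 5.12, name the ANCOVA without interaction (treatment, region as randomized, age, baseline FMA-UE) as the primary model whatever the interaction result. Report the interaction p-value against 0.10 and the region-specific effects from a separate supportive model, which still evaluates the interaction as Section 5.2 requires. Apply the same to the Day 90 FMA-UE secondary and to the repeated-measures sensitivity analysis, which inherits the ANCOVA's terms.

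If the sponsor prefers to keep the two-step rule, the minimum is to name the subject-weighted contrast for the case where the term is kept. That gives 5.0–5.1% with power unchanged at 81%.

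Use one region label in the same edit: Section 5.7 says US and UK, while Sections 3.1 and 5.2 say North America and ROW. This is a wording point and does not affect the figures.

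The cost is about two sentences and no power under a uniform effect. The one downside is that the interaction no longer alters the primary test. Given the FDA discussions recorded in Section 5.2, the regulator should be notified.
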